Statistical Analysis Plan

Epidural Steroid Injection with Supplemental Oral Eplerenone for Low Back Pain: A Prospective, Double Blind Randomized Trial

Principal Investigator: [name]

Project Sponsor: Department of Anesthesiology, University of Cincinnati College of Medicine

UC IRB Number: 2017-2713

[figure not shown]
IRB Approval Date(s): 10/11/2017

SAP Date (PI Signature Date): 1-17-18

Version: Original

Statistician(s): [name]

[figure not shown]
This SAP has been reviewed and approved by:

[name], Principal Investigator

1-17-2018

Date

[name], Statistician

1-17-2018

Date

A. Introduction:

Low back pain is a leading cause of disability and health care costs in the United States, and treatments are ineffective for many patients. Epidural steroid injections are a common treatment, but their efficacy has been questioned and for many patients they do not provide complete relief. We hypothesize, based on preclinical studies, that lack of complete efficacy may be due to the fact that clinically used steroids activate not only the intended drug target, the glucocorticoid receptor (GR), but also the pro-inflammatory mineralocorticoid receptor (MR). To test this hypothesis, this pilot study will recruit patients scheduled for lumbar epidural steroid injections for degenerative disc disease, and randomize them to receive a concurrent treatment with oral eplerenone (a clinically approved antagonist of the mineralocorticoid

receptor) or placebo for 10 days starting just after the epidural injection. The primary outcome will be improvement in treatment outcome as measured by the Oswestry Low Back Pain Disability Questionnaire, a validated research instrument that investigates both pain and functional outcomes. Subjects will be followed for one year. Secondary outcomes include the clinical course, in particular, whether the patient requires additional injections or not as part of their routine clinical care.

B. Specific Aims and Hypotheses

Aim 1: Test the hypothesis that subjects receiving eplerenone will show greater improvement in the Oswestry Low Back Pain Disability Questionnaire 12 months after the epidural steroid injection than subjects receiving placebo (primary outcome measure).

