Eplerenone and placebo pills with blinded labels will be provided by Investigational Drug Pharmacy. We will use a block-stratified randomization schedule with blocks of sizes 2 and 4. The West Chester and Uptown locations will have separate randomization schedules. Patients will be randomized to receive either eplerenone or placebo, which will be taken for 10 days starting two days after the epidural injection. The dose of eplerenone will be 50 mg PO daily. Eplerenone is extensively metabolized with less than 5% excreted unchanged in the urine. Thus, renal dysfunction has little effect on eplerenone pharmacokinetics. However, patients with compromised renal function may be at greater risk for hyperkalemia when taking eplerenone. For this reason, a blood sample will be obtained from each participant to verify inclusion criteria related to kidney function (see below) based on a basic metabolic panel performed the day of the procedure. Subjects with elevated potassium or creatinine will not be included in the study. The blood sample will be obtained just prior to the epidural injection, at the clinical laboratories located within (West Chester site) or adjacent to (Midtown clinic) the participating pain clinics. This will allow the results (metabolic panel including K⁺ and creatinine level) to be available by the following day. In order to avoid having subjects make an additional trip to the clinic, subjects will receive their study medications via overnight delivery service, once their blood test

results have been reviewed. Alternatively, subjects who prefer may return to the clinic to pick up their medications. A single take-home sheet of information about the study medication will be given to each patient along with the medication, to help reinforce these directions. We anticipate that few subjects will be excluded on the basis of their blood test.

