Patients are normally seen for follow-up approximately one month after an epidural injection. Subjects who are recommended to have a second epidural injection at this follow-up visit will receive a second dose of the same study medication they received after their first injection. The same protocol will be followed: such subjects will have a repeat blood draw and re-confirmation of inclusion parameters prior to restarting the medication. Subjects who become ineligible at the time of the second injection will not receive a second round of study medication, but will continue to complete questionnaires and their data will be retained for analysis.

All patients will receive the same epidural steroid and approach (interlaminar injection of Kenalog (triamcinolone) and saline) as part of their standard care. Triamcinolone has a substantial potency for the MR in addition to the GR; all of the steroids commonly used for epidural injections show some activity at the MR. The procedures and drug are routinely used at the participating clinics for treatment of degenerative disc disorders.

We will use the REDCap (Research Electronic Data Capture) system for secure web based capture of questionnaire data, which is required in order to protect the confidentiality of the subjects' data.

Inclusion criteria:

- Adult patients of either sex, age 18 to 65
- Scheduled for lumbar epidural steroid injection as part of routine clinical care
- Have a diagnosis of lumbar degenerative disc disease demonstrated on either lumbar X-Ray or lumbar MRI.
- Have unilateral radicular symptoms or electromyograph consistent with radiculopathy and exam findings corresponding to this diagnosis: with symptoms reflecting a dermatomal distribution of pain and positive response to straight leg raise test, which is known to be a sensitive, but not specific test for nerve root irritation.

Exclusion criteria: Excluded from the study will be patients with medical contraindications, including specifically those related to use of eplerenone:

- Unable to complete questionnaires or give informed consent in English
- Unavailable for follow-up contacts to complete questionnaires
- Renal impairment (estimated glomerular filtration rate (GFR)<50 mL/min or serum creatinine >1.8mg/dL) on metabolic panel obtained just prior to epidural injections.
- Elevated serum potassium (>5.5 mEq/L) on metabolic panel obtained just prior to epidural injections.
- Have undergone previous lumbar surgery.

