- Treated with oral steroids or injectable steroid within the past year.
- Diabetic
- Systolic blood pressure reading less than 100 mm Hg at most recent clinic visit.
- Prescribed protease inhibitors, a class of antiviral drugs widely used to treat HIV/AIDS and Hepatitis C.
- Taking strong CYP3A4 inhibitors
- Taking potassium supplements or potassium-sparing diuretics (amiloride, spironolactone, or triamterene) or using salt substitutes that contain potassium
- Lactating.
- Pregnant
- .

D. Statistical Analysis Plan

For categorical variables, counts and percentages will be presented. As a check on randomization, groups will be compared using the Fisher's exact test. For continuous variables, mean, median, standard deviation (SD) and inter-quartile range (IQR) will be presented. Groups will be compared using the t-test, except that non-parametric methods will be used for ordinal variables or variables distributed non-symmetrically.

D1. Aims 1 and 2:

Each Oswestry response has 6 ordinal response choices scored 0 through 5. With 10 items and with the lowest score (0) representing the least disability, the total raw score ranges from 0 to 50. The score is expressed as a percentage of the maximum possible score. If a subject omits one question, the percentage score is based on a maximum score of 45. If a subject omits more than one question the questionnaire is considered invalid and the data not used. Improvement scores are calculated by subtracting the score at a given time point from the score obtained prior to the first epidural steroid injection. Group differences in the improvement scores at the 12 month time point and at the intermediate time points will be analyzed using the Mann-Whitney test.

Patients who are withdrawn from the study due to the initial blood test results will be considered as screening failures; no follow-up data or questionnaire scores will be obtained.

D2. Aim 3: The clinical outcome of the first epidural steroid injection will be abstracted from the medical chart record of the follow-up visit that occurs approximately 1 month after the injection, and will be summarized as an ordinal variable scored as: 1 adequate pain relief, no further treatment recommended; 2, partial relief, second injection recommended; 3 little pain relief, alternative treatment recommended.

Demographic data will be compared between the groups to determine if values differ significantly despite randomization (table 1 below).

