E. Variables in the analysis data set

Patient unique ID
Age at first epidural steroid injection (years)
Date of epidural steroid injection
Weight and height at time of epidural steroid injection
Date of enrollment
Gender
Race
Ethnicity
Randomized to control or experimental group?
Oswestry scores (prior to first injection, 2 week, 3, 6, and 12 month post first injection)

F. Variables to Create / Calculate

BMI
Change in Oswestry score (score at each time point minus baseline score)

G. Data Sources

- EPIC chart review
- Oswestry scores exported from REDCap (baseline, 2 week, and 3, 6, and 12 month after first epidural steroid injection)

H. Software Used (with References) and Specialized Macros (with References)

Calculation of basic statistical parameters, t-tests, Mann-Whitney tests, and Fischer's exact test will be conducted using GraphPad Prism (GraphPad Software, Inc.) or SAS 9.4 (SAS Institute).

I. Mock tables to be produced

Table 1: Descriptive table of demographics of experimental and control groups prior to intervention.

Description	Control (N = ***) ¹	Experimental (N = ***) ¹	p value
Age at time of first injection (years)			
Weight at time of first injection			
Height at time of first injection			
BMI at time of first injection			
Race			
Ethnicity			
Oswestry score at first injection			

¹Mean, SD, median, interquartile range for continuous variables, number and % per group for categorical variables.

Table 2 Pain and disability outcomes

Description	Control (N = ***)	Experimental (N = ***)	p value
Change in Oswestry score at 2 weeks after injection			
Change in Oswestry score at 3 months after first injection			
Change in Oswestry score at 6 months after first injection			
Change in Oswestry score at 12 months after first injection			
Clinical outcome of first injection ³			

³ Converted to ordinal scale 1 – 3

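### The 12-month Mann-Whitney test is valid, but it uses baseline only by subtraction, ignores the clinic stratum, and comes with no planned between-group estimate or interval

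*SAP*

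**What the plan says.** - **Outcome and test.** SAP Aim 1 makes the 12-month Oswestry comparison primary. SAP D1: "Improvement scores are calculated by subtracting the score at a given time point from the score obtained prior to the first epidural steroid injection". The arms are then compared with a Mann-Whitney test ("improvement scores at the 12 month time point and at the intermediate time points will be analyzed using the Mann-Whitney test"). Protocol section 12 names the same test because the scale is ordinal. SAP section D gives a matching general rule: "non-parametric methods will be used for ordinal variables or variables distributed non-symmetrically".
- **Baseline.** Apart from the subtraction, baseline Oswestry appears only as a balance row in mock Table 1.
- **Clinic.** SAP section C: "The West Chester and Uptown locations will have separate randomization schedules". Clinic is absent from D1, from the variable lists in sections E and F, and from both mock tables. Section E does list treatment arm ("Randomized to control or experimental group").
- **Output.** SAP section D: "For continuous variables, mean, median, standard deviation (SD) and inter-quartile range (IQR) will be presented". Mock Table 2 has a column for each arm and a p value, with no column for a difference or an interval.
- **Sign of change.** D1 takes baseline minus follow-up. Section F takes follow-up minus baseline.

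**The concern.** Two pieces of information that the trial will already hold, the baseline score and the clinic, are left out of the comparison or used inefficiently. Subtracting baseline assumes that a one-point difference at baseline carries through as one point at 12 months. If the true slope is lower, the change score carries avoidable noise. If the clinics differ in average improvement, that variation stays in the comparison although randomisation was balanced on it.

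The missing estimate matters whatever the power. Protocol section 12 frames the trial in points: a 9-point target, and thresholds for clinical significance from 4 to 15. A p value cannot place the result on that scale. A pilot intended to lead to multicentre trials (Protocol section 9) is most useful if it reports how large the difference is and how uncertain.

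**Working it through.** **1. The plan's own figure.** Inputs from Protocol section 12: 20 per group, difference 9, SD 10, alpha 5% (two-sided assumed).
- Standard error = 10 × √(2/20) = 3.162, and 9/3.162 = 2.846.
- Power = Φ(2.846 − 1.960) = Φ(0.886) = 81%.
- The t-test gives 79%. Mann-Whitney gives 79% by its asymptotic efficiency of 3/π and about 77% by simulation.

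The stated 80% is reproduced.

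**2. What baseline adjustment can gain.** Let ρ be the baseline-to-12-month correlation and k the 12-month SD divided by the baseline SD. The documents give neither. Take SD 10 as the change-score SD (an assumption).
- Slope of the 12-month score on baseline = ρk. Subtraction is fully efficient only when ρk = 1.
- Adjusted variance / change-score variance = k²(1 − ρ²) / (1 + k² − 2ρk).
- Example, k = 1, ρ = 0.5: 0.75/1 = 0.75.
- Example, k = 1.5, ρ = 0.7: 1.1475/1.15 = 0.998, so almost no gain.

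**3. Simulated power.** Normal residuals, 10 per arm per clinic, no clinic difference, 20,000 or more trials per cell. The adjusted rank test regresses the 12-month score on baseline and site, then applies Mann-Whitney to the residuals. The linear model regresses the 12-month score on treatment, baseline and site. The planned test has about 77% power in every cell.

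| k | ρ | variance ratio | adjusted rank | linear model |
|---|---|---|---|---|
| 1 | 0.3 / 0.5 / 0.7 | 0.65 / 0.75 / 0.85 | 91 / 87 / 83% | 92 / 88 / 84% |
| 1.25 | 0.3 / 0.5 / 0.7 | 0.78 / 0.89 / 0.98 | 85 / 81 / 78% | 87 / 82 / 79% |
| 1.5 | 0.3 / 0.5 / 0.7 | 0.87 / 0.96 / 1.00 | 82 / 78 / 77% | 83 / 79 / 78% |

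**4. Other residual shapes, same ρ and k.**
- With t(3) or skewness-2 residuals, the adjusted rank test runs from about 12 to 13 points better than the planned test to about 1 to 2 points worse. The losses occur where ρ is high and k exceeds 1.
- The linear model falls as much as 12 points (t(3)) or 14 points (skewness 2) below the planned test.
- Example, t(3), k = 1.25, ρ = 0.5: planned 93%, adjusted rank 95%, linear 86%.
- Type I error of the adjusted rank test is about 5 to 5.5%.

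**5. Clinic.** ρ = 0.5, k = 1, normal residuals, assumed clinic difference in improvement of 0, 5 or 10 points:
- Planned test: power 77, 75 and 68%; type I error about 5.1, 4.2 and 2.8%.
- Adjusted rank test: power about 87% in all three.

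**6. Interval width.** Unadjusted 95% half-width = 2.024 × 3.162 = 6.4 points. The linear model gives 5.2 / 5.6 / 6.0 at k = 1 and 6.0 / 6.3 / 6.45 at k = 1.5, for ρ = 0.3 / 0.5 / 0.7. For illustration, an observed unadjusted difference of 5 would span 5 ± 6.4, or −1.4 to 11.4: not significant, yet compatible with more than the 9-point target.

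**The case against.** The strongest reply is that this is a choice between valid methods. The plan gives a reason for ranks, its power figure reproduces, and any gain depends on quantities the documents do not state. That stands, and it limits the point to efficiency and reporting. Four further points also stand.

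- **Linear model as primary test.** A reader might infer that a linear model should replace the rank test. The documents do not support that. Across the shapes checked, its effect on power runs from about +15 to −14 points, and section D provides for non-symmetric variables. Part of its gain under normality comes from leaving ranks: an unadjusted t-test already has 79% against 77%.
- **Clinic.** A reader might infer that ignoring the stratum inflates false positives. It does not: the test keeps its level or becomes conservative. No passage suggests a clinic difference, and SAP section C says "All patients will receive the same epidural steroid and approach". The 5- and 10-point shifts and the equal clinic split are assumed. Section E is also not exhaustive: it omits the Aim 3 clinical outcome, which D2 and Table 2 use.
- **No effect size at all.** That would overstate. If the section D summaries are applied to the change scores, N, mean and SD per arm let a reader build the crude ±6.4 interval. What is missing is a prespecified, adjusted contrast with a fixed direction.
- **Meaning of SD 10.** Protocol section 12 does not say whether it is the SD of scores or of changes. If it is the single-score SD (k = 1), the linear model's gain over Mann-Whitney is about 20 / 11 / 3 points at ρ = 0.3 / 0.5 / 0.7, instead of 15 / 11 / 7.

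The ordinal argument does not rule out a mean difference as the estimate. The plan already converts the total to a percentage, subtracts scores and sets its power in points with an SD.

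**Conclusion.** The point holds as one of efficiency and reporting, not error. The planned test is valid with complete data. Adjusting a rank test for baseline and clinic would raise power from about 77% to between 77 and 91% under normal residuals. Across all the shapes checked, it costs at most about 2 points. The gain is close to nil when ρk is near 1. These figures rest on 20 per arm, a 9-point difference, change SD 10, ρ of 0.3 to 0.7 and k of 1 to 1.5, and the documents do not give ρ or k. The clinic part is worth nothing unless the clinics differ. With an assumed 10-point difference, the planned test falls to about 68% power and 2.8% type I error. The lack of a prespecified between-group estimate and interval depends on none of these assumptions and is the firmest part. The change is worth making; confidence in the size of the gain is moderate.

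**What to change.** Before unblinding:

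1. In SAP D1, keep a rank-based primary test but adjust it for baseline score and site. For example, regress the 12-month score on baseline and site with the arms pooled, then apply Mann-Whitney to the residuals; an equivalent rank ANCOVA would also do.
2. Report the treatment difference with 95% CI from a linear model of the 12-month score on treatment, baseline and site. State that the rank test decides significance, since the two methods may occasionally disagree.
3. Keep the unadjusted Mann-Whitney test on change scores as a prespecified sensitivity analysis.
4. Add site to SAP section E and an estimate with 95% CI column to Table 2. When coding site, reconcile the labels: the randomisation text says Uptown where the clinic description says Midtown.
5. Use one sign convention for change in D1 and section F.
6. Make the same change in Protocol section 12, so that the two documents do not conflict.

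**Cost.** A protocol and SAP amendment, one variable already known from the randomisation schedules, one table column and a short program in SAS 9.4, which the SAP lists. No new data or patients are needed. The downside is a possible power loss of about 1 to 2 points if the baseline correlation is high and the 12-month SD exceeds the baseline SD.
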